#### V. STUDY DESIGN

This is a prospective, single arm, nonrandomized, early feasibility study to evaluate the safety and performance of the Harpoon Medical Device.

#### VI. STUDY POPULATION

##### NUMBER OF PATIENTS

Up to 20 patients in PL may be enrolled. The estimated enrollment period is 24 months, and all patients shall be followed for 30 days, 6 months, 12 months and 24 months after implantation in accordance with the Clinical Investigations schedule provided in Section VIII.

## INTENDED USE

The Harpoon Medical Device is intended to be used by a trained medical professional. The device is designed to reduce the degree of mitral regurgitation by delivering and anchoring artificial chordae tendineae to the affected mitral valve leaflet(s) in a beating heart. The device is intended to be a Single Use Device, used in a surgical operating suite or equivalent setting.

## INCLUSION CRITERIA

- Age  $\geq$  18 years
- Patient referred for mitral valve surgery
- Presence of severe MR as read on an echocardiographic study performed within 60 days prior to procedure.
- Estimated post-ePTFE chordae tendineae implantation coaptation surface is adequate in the judgment of the operating surgeon and the patient eligibility committee
- Degenerative mitral valve disease associated with anterior, bileaflet, or posterior leaflet prolapse
- Patient is able to sign informed consent and able to return for follow-up and is capable of participating in all testing associated with this clinical investigation
- Women of child-bearing potential have a negative pregnancy test

## EXCLUSION CRITERIA

- Age < 18 years
- Infective endocarditis
- History of Mediastinal Radiation
- Inflammatory (rheumatic) valve disease
- Requirement for concomitant cardiac surgery (e.g., coronary artery bypass grafting (CABG), aortic valve surgery, etc.)
- Symptomatic coronary artery disease
- Cardiogenic shock at the time of enrollment
- ST segment elevation myocardial infarction requiring intervention within 30 days prior to enrollment
- Evidence of cirrhosis or hepatic synthetic failure
- Pregnancy at the time of enrollment (women of child bearing age should have negative pregnancy within 14 days of surgery)
- Severe pulmonary hypertension (PA systolic pressure > 70 mmHg)
- Previous cardiac surgery, or surgery on the left pleural space
- Left ventricular, atrial or appendage thrombus
- Severely calcified mitral leaflets
- Recent stroke (< 6 months) with permanent impairment
- EuroScore (for mitral valve repair) > 8%
- Patients with contraindications to Transesophageal echocardiography
- Severe left or right ventricular dysfunction
- NYHA Class IV
- Renal insufficiency CKD stage 3b or worse (GFR < 45 ml/min/1.73 m^2)
- Patient is participating in another clinical study for which follow-up is currently ongoing. (Co-enrollment in an investigational device or interventional study)

- Patient with non-cardiac co-morbidities and life expectancy < 1 year  
Patient has a condition or conditions that, in the opinion of the Investigator, preclude participation, including willingness to comply with all follow-up procedures

## VII. PATIENT ENROLLMENT

### PRE SCREENING

**Screening evaluations:** All patients that are identified as potential candidates for the study shall undergo transthoracic echocardiography (TTE). This echo should have been performed within the two months preceding the patient's inclusion in the study.

A TEE will be performed at the referring doctor's request. Both the TTE and TEE are routinely performed in patients undergoing heart valve surgery.

If the patient is deemed to be a good candidate for the study, the investigator will ask him to sign the Echo PIC to release existing medical records to the Harpoon Patient Eligibility Committee (PEC) for review and evaluation for enrollment. These records include the screening evaluations (anonymized echocardiogram along with the limited medical information (age, vital signs)).

The PEC will provide the study site with a Pass or Fail for the patient being screened.

If the PEC determines a PASS for the patient under consideration, Harpoon Medical will validate the participation and the patient will be asked to sign the study informed consent and, once officially enrolled, will proceed to the pre-procedure/baseline evaluations.

If the PEC determines a FAIL for the patient, the patient will be referred back to the standard of care. If the patient data is not satisfactory for the PEC, the PI may request a new echo be completed if this falls under standard practice. This new echo will then be submitted to the PEC for re-evaluation. All data received by the PEC for this patient will be destroyed. Only data compiled in screening enrollment log will remain.

In any case, the PEC will provide the site with an MDDX number for each patient reviewed. The site will be asked to maintain a list of these numbers and the related patients. This information will be reported on a Screening and Enrollment log maintained in the study file on site. The MDDX number is composed of two digits for site number and two digits for patient number. Only one number will be given per patient and will remain the same if the patient is further enrolled.

### INFORMED CONSENT

Patients who have been pre-screened and for whom the principal investigator feels would be a good candidate for inclusion in the Trial, will be asked to sign the study specific Ethics Committee (EC) approved Patient Information Sheet before any study-specific tests or procedures are performed. Enough time will be given to the patient (at least 24h) to read and understand the informed consent form and to consider participation in the clinical investigation.

The PI (or one of his co investigators specifically identified on the delegation log and authorized to do so) will answer all patients' questions and will clearly explain to the patients that even if they agree to participate in the study and sign the Patient Information Sheet, they can withdraw their

consent to participate at any time. They will continue to be followed and treated by the site as normal. The site personnel will make sure also that the patients have understood what their participation means (visits and tests scheduled) and that even if they sign the consent they may not be eligible to participate if he/she fails additional eligibility criteria.

The Screening/Enrollment Log is maintained in the on-site clinical records located at the study site to document select information about candidates who pass or fail to meet the entry criteria. In the case a patient does not want to participate to the study, the PEC will destroy the data transferred.

## ENROLLMENT

Point of enrollment: a patient will be officially considered as enrolled after consent has been signed and dated by him/her. The patient will be followed until his/her study exit (study completed, withdrawal, lost to follow up, death). All the events will be registered from that date and until the patient leaves the study for one of the reasons previously mentioned.

One original form will be kept on site (in patient's medical records) and one will be provided to the patient. The version kept on site will be reviewed by the clinical monitor during the monitoring visit to ensure that the correct version has been signed and that the consenting process has been respected.

The site staff will also make sure that the patient study participation is clearly indicated in patient's files.

## PRE-PROCEDURE/BASELINE EVALUATIONS

Once the patient is officially enrolled for the Harpoon Medical study, a Physical Assessment will be performed. This includes:

- Vital signs
- 12-lead ECG
- Routine Laboratory assessment (including WBC count; Hemoglobin; hematocrit; platelet count; creatinine Level, INR)
- Additional Laboratory assessment (including Total Albumin, Total Bilirubin, BNP, NTproBNP)
- A chest radiograph (X-Ray)
- A serum pregnancy test for females with childbearing potential (age < 50 years) shall be completed within 14 days prior to the procedure
- In accordance with the hospital's clinical Standard of Care, a left heart catheterization (LHC) may be required for all patients  $\geq 45$  years of age without risk factors and for any patient with symptoms of coronary artery disease
- Pulmonary Function Tests, when clinically indicated
- 6 Minute Walk test
- Quality of Life Assessment
- EUROscore assessment

The data from this physical assessment shall be recorded on a Case Report Form (CRF).

## TREATMENT PROCEDURE/ASSESSMENTS

The procedural approach requires that the patient be administered a general (single lumen) endotracheal anesthesia with appropriate monitoring lines (e.g. arterial line) and heparinized saline to achieve an activated clotting time of  $\geq 350$  seconds. The patient should be placed in the supine position with elevation of the left hemithorax to 30°. Briefly, the procedure consists of performing a small left lateral thoracotomy incision overlying the left ventricular apex, opening the pericardium and selecting an insertion site on the epicardium for the Harpoon Medical device where a monofilament purse-string suture is placed to hold the Harpoon device introducer in place and reduce bleeding. Once the introducer is in place, the device is inserted and positioned adjacent to the mitral leaflet under TEE guidance and bulky suture knot is deployed to secure paired sutures in the leaflet. The paired sutures are brought outside the ventricle. Up to four (4) suture pairs may be placed, using a single valved introducer (TAV-5), to secure and align apposition between the anterior and posterior mitral leaflets. If more than four (4) suture pairs are required, the TAV-5 must be removed and reinserted for reuse, and then an additional four (4) suture pairs may be inserted. Once an adequate number of suture pairs are placed, the device and introducer are removed, and the suture pairs are tightened and secured to the exterior myocardium using pledgets for each suture pair. The thoracotomy should be closed, and chest tube(s) should be inserted, per hospital standard of care.

The details of the procedure are described thoroughly in the Harpoon Medical Device Instructions for Use.

If in the judgment of the operating surgeon, adequate MR reduction has not been achieved, or if for any other clinical reason, conversion to SOC mitral valve surgery via a median sternotomy shall be performed. This procedure may be performed at the time of the Harpoon Medical procedure or at a later date/time at the discretion of the operating surgeon.

#### FOLLOW-UP PROCEDURES/ASSESSMENTS

**Post-procedure management:** Standard hospital protocols for the management of patients after mitral valve surgery shall be followed. Unless other indications for anticoagulation are present, all patients shall receive only 325 mg/day low dose aspirin, beginning on arrival to the intensive care unit).

**Discharge:** All patients shall be discharged from the hospital at the discretion of the attending cardiac surgeon.

For the patients where a procedure was finally not started (i.e. echo results) or started but finally interrupted with no use of the study device, the discharge date will be registered as the study termination date and no more data will be collected for these patients.

For the patients where a procedure attempt has been made, Harpoon device used, but procedure was finally not completed and patients were converted to another treatment a safety period of 30 days post procedure will be required. Clinical data will be collected and CRF completed until that date. The 30 days Follow up date will be registered as the study termination date for these patients.

For the patients successfully treated, the expected follow period is 24 months. Patients will be followed until that date except under certain circumstances (withdrawal, death, lost to follow up).

Prior to dismissal all patients shall undergo a comprehensive pre-dismissal TTE, as well as a physical assessment (vide supra) in accordance with the schedule of Clinical Investigations.

**Patient follow-up:** The expected follow up period after the Harpoon procedure is from 24 months. Assessments will be completed at 30days, Discharge, 6 months, 12 months and 24 months.

30 days follow up (+10/0 days post procedure) - Patients will be seen in the outpatient clinic and the following exams will be performed:

- Physical exam, including NHYA evaluation if needed
- ECG
- TTE AE evaluation
- Concomitant medication changes

6 months follow up (+/- 30 days) - Patients will be seen in the outpatient clinic and the following exams will be performed:

- Physical exam, including NHYA evaluation if needed
- TTE
- AE evaluation
- Concomitant medication changes

12 months follow up (+/- 30 days) - Patients will be seen in the outpatient clinic and the following exams will be performed:

- Physical exam, including NHYA evaluation if needed
- 6 minute walk test (6MWT)
- SF36 questionnaire
- TTE
- AE evaluation
- Concomitant medication changes

24 months follow up (+/- 30 days) - Patients will be seen in the outpatient clinic and the following exams will be performed:

- Physical exam, including NHYA evaluation if needed
- TTE
- AE evaluation
- Concomitant medication changes

The table below summarizes the general and cardiac assessments and expected follow up.

General Assessment	PL study site Responsibility	Harpoon Medical Responsibility	Screening and pre-operative evaluation	Surgery Date	Discharge	30 Days (+ 10/-0 d)	6 Months (+/- 30 d)	12 Months (+/- 30 d)	24 Months (+/- 30 d)
Invitation to enroll in the study	X		X						
Screening worksheet completed	X		X						
Patient Eligibility Committee Assessment		X	X						
Patient Information Sheet Signed	X		X						
Pre-Procedure worksheet completed	X		X						
Release of Medical Information **	X		X						
Medical History **	X		X			X	X	X	X
Medications & Dosage **	X		X	X	X	X	X	X	X
Physical Exam **	X		X		X	X	X	X	X
Laboratory Assessment (blood work)	X		X						

\*\* - included as part of the baseline/pre-procedure worksheet

Cardiac Assessment	PL study site Responsibility	Harpoon Medical Responsibility	Screening and pre-operative evaluation	Surgery Date	Discharge	30 Days (+ 10/-0 d)	6 Months (+/- 30 d)	12 Months (+/- 30 d)	24 Months (+/- 30 d)
Chest Radiograph (X-Ray)	X		X						
Diagnostic Left Heart Catheterization or Clinical Standard of Care	X		X						
NYHA Heart Failure Class	X		X			X	X	X	X
Electrocardiogram (ECG)	X		X			X			
Transthoracic Echocardiogram (TTE) ***	X		X		X	X	X	X	X
Transesophageal Echocardiogram (TEE)	X		X	X					
SF-36 Quality of Life Assessment	X		X					X	
6 Minute Walk Test	X		X					X	
EUROscore risk assessment	X		X						
Pulmonary Function Test (if clinically indicated)	X		X						

\*\*\* TEE: may be required if the TTE images are not readable

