## DURATION OF INVESTIGATION

The estimated duration for the main investigational plan (e.g. from start of screening to last participant processed and finishing the study) is approximately 36 months.

Each patient will be followed for 24 months and then exit the investigation. It is anticipated that all clinical investigation patients will be enrolled within a 24 month time period.

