## VIII. SAFETY MANAGEMENT

Subjects will be carefully monitored during the study for possible Adverse Events (AEs) from the time the Subject signs the Patient Informed Consent form to the completion of their participation in the study. Any AE observed will be fully investigated by the Investigator and classified in line with the definitions of the ISO14155:2011 below.

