## **X. STATISTICAL ANALYSIS**

This is an early feasibility study. The sample size for this study was determined from the first early feasibility study for this device for the treatment of mitral regurgitation at the conclusion of the procedure and at the time of the hospital dismissal and at one year. Specifically the percentage of patients that demonstrate MR reduction from severe to </+ moderate at the conclusion of the procedure and at 30 days. These data will be used to assess the safety and performance of the device when used on a human patient. These data will be used to assess initial safety and performance of the Harpoon Medical Device, and are not designed to test a statistical hypothesis, therefore a formal sample size has not been calculated. All data will be captured on an intent-to-treat basis. Data will be reported as descriptive statistics.

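### Follow-up length depends on procedural outcome, which conflicts with the intent-to-treat statement and leaves the 6-, 12- and 24-month denominators unstated

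*Combined protocol and SAP*

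**What the plan says.** Section X (Statistical Analysis) states: "All data will be captured on an intent-to-treat basis". Results are to be descriptive, and no formal sample size was calculated. Section VII (Enrollment) counts patients in before any procedure: "a patient will be officially considered as enrolled after consent has been signed and dated by him/her". Duration of Investigation adds: "Each patient will be followed for 24 months and then exit the investigation".

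The discharge text in Follow-up Procedures/Assessments sets three different lengths of follow-up:

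- Procedure not started, or started and interrupted without device use: "the discharge date will be registered as the study termination date and no more data will be collected for these patients".
- Incomplete procedure after use of the device: "but procedure was finally not completed and patients were converted to another treatment a safety period of 30 days post procedure will be required". The exit rule for this group reads: "The 30 days Follow up date will be registered as the study termination date for these patients".
- Treatment regarded as a success: "For the patients successfully treated, the expected follow period is 24 months".

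Treatment Procedure/Assessments calls for conversion to standard surgery when the surgeon judges MR reduction inadequate, or for another clinical reason. It allows this in the same session or later. Section IV (Endpoints) makes MR severity and freedom from SAEs at 6, 12 and 24 months secondary endpoints, and makes 30 days a primary time point for both performance and safety. Section VIII monitors adverse events "from the time the Subject signs the Patient Informed Consent form to the completion of their participation in the study". No section defines an analysis set, a denominator at the late visits, or how early exits are counted.

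**The concern.** All three groups are enrolled, because all have consented, yet the length of observation is decided by what happened in the operating room. Inadequate MR reduction is itself a stated reason for conversion, so a patient can leave the late data because the device failed on the performance measure. Late results from those still followed would then describe patients selected by procedural outcome, under an intent-to-treat label.

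The two late endpoints are affected differently. For MR, echocardiograms after conversion would assess a different operation, so the question is how converted patients are counted. That can be settled at analysis without further data. For SAEs, events that nobody records cannot be restored at analysis. In a descriptive study of up to 20 patients the reported proportions are the result, so it matters who is in them.

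**Working it through.** **Which statements conflict.** The Study Summary (Follow-up) and Number of Patients count the visits to 24 months from implantation. That is compatible with the shorter follow-up of patients who received no implant. Duration of Investigation (each patient, 24 months) and Section X (all data, intent-to-treat) have no such qualifier and do not fit the discharge rules. Enrollment lists the exits as completion, withdrawal, loss to follow-up and death; conversion and non-use of the device are not among them.

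**What is not collected.**

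1. *Converted after device use, exit at day 30.* New SAEs after day 30 are not collected. The adverse-event text under How to report has the investigator follow events until they resolve or become chronic, so events already under way at exit are arguably still covered. If freedom from SAEs is cumulative, a converted patient with an SAE by day 30 is already a non-success at 6, 12 and 24 months. Only converted patients who are SAE-free at day 30 have unknown late status.
2. *Operation started, device not used, exit at discharge.* Day-30 safety and performance data are not collected, although both belong to primary endpoints. The group is probably small: Device Description counts the valved introducer as part of the device, so inserting it is arguably device use and would bring the 30-day rule into play.
3. *Unassigned cases.* A later conversion could be read as converted, with exit 30 days after a procedure that is not specified, or as completed, with 24 months. A completed procedure that was not successful, a term left undefined, meets neither early-exit rule, but is not expressly given 24 months either.

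**How likely a conversion is.** The plan states no expected rate. The Summary of Preclinical Studies reports no procedural conversion in 13 patients of the sponsor's previous feasibility study. The exact 95% upper bound is 1 − 0.025^(1/13) = 24.7%, or 0.247 × 20 = 4.9 patients in 20. With an assumed true rate p, the chance of at least one conversion in 20 is 1 − (1 − p)^20: 33% at p = 2%, 64% at 5% and 88% at 10%.

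**Late MR success (assumed counts).** Let 20 operations be started, c converted, and f of the others fail late. The followed-only rate is (20 − c − f)/(20 − c). The rate over all started, with conversions as failures, is (20 − c − f)/20. The gap equals the followed-only rate times c/20, so it is at most 5 points per conversion. Exact (Clopper-Pearson) 95% intervals are in brackets.

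| c | f | Followed only | All started | Gap |
|---|---|---|---|---|
| 0 | 0 | 20/20 = 100% (83.2–100) | 20/20 = 100% (83.2–100) | 0 |
| 1 | 0 | 19/19 = 100% (82.4–100) | 19/20 = 95% (75.1–99.9) | 5.0 points |
| 2 | 0 | 18/18 = 100% (81.5–100) | 18/20 = 90% (68.3–98.8) | 10.0 points |
| 2 | 2 | 16/18 = 88.9% (65.3–98.6) | 16/20 = 80.0% (56.3–94.3) | 8.9 points |
| 4 | 0 | 16/16 = 100% (79.4–100) | 16/20 = 80% (56.3–94.3) | 20.0 points |

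**Late freedom from SAEs (assumed counts).** Take c = 2 and 3 of the 18 followed patients with an event.

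- Followed only: 15/18 = 83.3% (58.6–96.4).
- All started, both converted patients with an event: (20 − 3 − 2)/20 = 15/20 = 75.0% (50.9–91.3).
- All started, neither with an event: (20 − 3)/20 = 17/20 = 85.0% (62.1–96.8).
- If both had an SAE by day 30 and the endpoint is cumulative, the result is known: 15/20.

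The followed-only figure lies inside the 75–85% range, so the issue for SAEs is unknown status and labelling, not a bias of known direction.

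**The case against.** The strongest reply is that no section says late rates will use followed patients only. Read plainly, the intent-to-treat sentence keeps converted patients in the denominator. The sponsor's own reporting points both ways: six-month MR in the previous study is given out of all 13, although one patient had been reoperated on day 72, while the one-year figures use the six patients with that visit. This stands. A reader might infer that the late rates will be inflated; the documents support only that the denominator is unstated and that collection is not intent-to-treat.

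A reader might also infer that all late safety information on converted patients is lost. That goes too far, since events under way at exit are arguably followed and an SAE by day 30 already settles a cumulative endpoint. Conversion may itself qualify as an SAE, although the note on protocol-required procedures in the SAE definition makes that arguable.

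The size is also hypothetical. No conversion occurred in 13 patients, the intervals overlap widely, and no test or threshold depends on the result. The two reoperations for recurrent MR in the previous study (days 72 and 231) followed procedures reported as successful, so they would not clearly trigger early exit. These points limit the size. They do not reconcile the discharge rules with Section X and Duration of Investigation.

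**Conclusion.** The point holds as a conflict in the current text with a practical consequence. If the discharge rules are followed exactly, the late data are not intent-to-treat, device failures can drop out of them, and the plan does not say how such patients count. Nor can a reader take day-30 primary performance as untouched, because patients whose operation was started without device use leave at discharge.

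The size is conditional. It is zero if nobody exits early. It is up to 5 points of late MR success per conversion among 20 if only followed patients are counted. For late SAE freedom it is one patient of unknown status for each converted patient who is SAE-free at day 30, if the endpoint is cumulative. All conversion and event counts are assumptions. Confidence is high on the mismatch and low on how large it would prove. It should be fixed, because SAE data not collected cannot be added later.

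**What to change.** - **Follow-up.** Reconcile the discharge rules, Duration of Investigation and Section X on who is followed and for how long. State which rule applies to a later conversion, from which procedure the 30 days run, and what applies to a completed procedure that was not successful.
- **Performance denominator (Section X).** At every time point, report over all patients whose operation was started, counting conversions and started-but-no-device cases as procedural failures. List consented patients whose operation never started separately in the patient accounting. Since enrolment is at consent, name this set for what it is.
- **Late SAEs.** Either continue SAE collection in converted patients to 24 months, or label the late rates as applying to successfully treated patients only, not as intent-to-treat. In the second case, state how many converted patients were SAE-free at exit and so have unknown late status. Say whether freedom from SAEs is cumulative.
- **Day 30.** Collect day-30 safety data for any patient whose operation was started, whether or not the device was used.

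The cost is wording in three places and a few extra contacts, with more contacts only if SAE collection is extended. Reported late rates become slightly less favourable if any patient is converted.

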##### Endpoints

**Primary Performance Endpoints:** To demonstrate that the Harpoon Medical Device performs as designed and can successfully implant one or more ePTFE artificial cords on either the anterior, posterior, or both leaflets of the mitral valve via a small left thoracotomy on the beating heart and reduce mitral regurgitation from “severe” to less than or equal to “moderate” at the conclusion of the procedure and at 30 days post-procedure.

**Secondary Performance Endpoints:** Severity of mitral regurgitation at 6 months, 12 months and 24 months follow-up shall be tracked and recorded

**Primary Safety Endpoints:** Procedure freedom from Serious Adverse Events (SAEs) during the procedure, at discharge, and at 30 days follow-up shall be tracked and recorded. Rates are expected to be not significantly worse than conventional mitral valve surgery.

**Secondary Safety Endpoints** Freedom from Serious Adverse Events (SAEs) at 6 months, 12 months and 24 months follow-up shall be tracked and recorded

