## END OF PARTICIPATION

Subjects who have finished the required follow-up visits will be considered to have completed the study.

Withdrawal: all patients have the right to withdraw themselves from participation at any point during the study. In addition, PIs also have the authorization to terminate a patient's participation in the study. A description of the reason for the patient's termination will be documented. Reasons for termination include: completion of study, patient's voluntary withdrawal, physician-directed patient withdrawal, and death.

Upon study exit the patient will be followed per standard of care by the investigator and/or another physician.

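### The 6-, 12- and 24-month MR summaries have no stated denominator and no rule for patients who are converted or have mitral reoperation

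*Combined protocol and SAP*

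**What the plan says.** Section IV (Endpoints) gives the secondary performance endpoint as "Severity of mitral regurgitation at 6 months, 12 months and 24 months follow-up shall be tracked and recorded". It sets no success threshold for these visits. Section X adds two general statements: "All data will be captured on an intent-to-treat basis" and "Data will be reported as descriptive statistics". Intent-to-treat is not defined further, and no denominator is given.

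Section VII (Follow-up Procedures/Assessments) sets three follow-up paths:

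- Procedure not started, or "started but finally interrupted with no use of the study device": the patient leaves the study at discharge.
- Device used, procedure not completed, patient converted to another treatment: "The 30 days Follow up date will be registered as the study termination date for these patients".
- Successfully treated (a term left undefined): 24 months of follow-up. "Patients will be followed until that date except under certain circumstances (withdrawal, death, lost to follow up".

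The exit list under Enrollment is similar. Neither list names mitral reoperation. Patient Withdrawal and End of Participation also let the physician take a patient out of the study, the latter listing "physician-directed patient withdrawal". Transthoracic echocardiography is scheduled at 6, 12 and 24 months.

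Treatment Procedure/Assessments allows conversion to standard surgery "at the time of the Harpoon Medical procedure or at a later date/time". The follow-up section does not say which path a delayed conversion takes.

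**The concern.** Conversion for inadequate MR reduction, and reoperation for recurrent MR, are failures of device performance. A later MR table should show them as such. As the plan stands, a converted patient has no later grade at all. A reoperated patient has either a grade that belongs to the surgeon's repair or no grade. Removing a failure and replacing it with a surgical result both push the table in the device's favour.

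The study enrols at most 20 patients and reports descriptively, so the proportion in the table is itself the durability result. With 20 patients, each one is worth 5 percentage points. If the rule is chosen after the failures are known, a reader cannot tell whether the choice was neutral.

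**Working it through.** **The plan's own figure.** There is none to reproduce. Section X states that no formal sample size was calculated, and no target rate is set for 6, 12 or 24 months.

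**How each type of failure enters the later MR tables**

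| Patient | Follow-up under the plan | Later MR tables |
|---|---|---|
| Converted, device used, procedure not completed | Ends at 30 days | Absent |
| Reoperated after a completed procedure | Appears to run to 24 months | Grade of the surgical repair |
| Reoperated, then withdrawn by the physician | Ends at withdrawal | Absent |
| Delayed conversion | Not stated | Not determinable |

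In no row does the patient appear as a device failure.

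**How often this may arise.** Section III (Summary of Preclinical Studies) reports two reoperations for recurrent MR among 13 patients, on postoperative days 72 and 231. Section VI gives a maximum of 20 patients here.

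- Rate: 2/13 = 15.4%. The exact (Clopper–Pearson) 95% limits are the 2.5% point of Beta(x, n−x+1) and the 97.5% point of Beta(x+1, n−x). With x = 2 and n = 13 they are 1.9% and 45.4%.
- Expected number in 20: 20 × 2/13 = 3.1.
- Chance of at least one at that rate: 1 − (11/13)^20 = 96.5%. At assumed rates of 5%, 10% and 25% it is 64.2%, 87.8% and 99.7%.
- Timing: both reoperations came after day 30, in the period with no rule. Day 72 precedes the 6-month visit. Day 231 falls after the 6-month window closes (about day 210) and before 12 months.

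**Effect on a 12-month table.** Assumptions: device used in all 20, all 20 otherwise observed, three reoperations, no conversions, and MR at most moderate in every other patient and after every repair. The cut at moderate is borrowed from the primary endpoint to show size only.

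- Reoperated patients kept and graded on the repair: 20/20 = 100% (95% CI 83.2–100).
- Reoperated patients left out: 17/17 = 100% (80.5–100).
- Reoperation counted as failure: 17/20 = 85% (62.1–96.8).

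Adding one conversion, also an assumption, gives 19/19 = 100% (82.4–100) if the converted patient exits and the reoperated patients are kept. It gives 16/20 = 80% (56.3–94.3) if all four count as failures.

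**The case against.** The strongest reply is that this is a small feasibility study with a secondary, purely descriptive endpoint, and that failures are visible elsewhere. A converted patient is first judged on the primary performance endpoint. An unplanned reoperation would ordinarily be a serious adverse event, freedom from which is reported at the same later visits, and an independent events committee reviews events. The sponsor disclosed both reoperations in the first study, with day and cause. MR grade among successfully treated patients is also a legitimate summary if labelled so.

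Most of this is true, and it limits the size of the point: no test or sample size is affected. It does not close the gap. Adverse event reporting does not put a failure into the MR table, and the plan does not label that table as restricted to successes. The intent-to-treat sentence does not help either, because it is undefined and the exit rules stop data collection for some enrolled patients.

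Some stronger readings are tempting but not supported:

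- *The plan says that reoperated patients are graded on the repair.* It does not. This is inferred from the exit lists and the echocardiography schedule, and physician withdrawal could remove the patient instead.
- *The first study's six-month counts already hid the reoperations.* Grades are given for 9 + 2 = 11 of 13 patients, but the documents do not say who the other two are. The day-231 reoperation came after that visit window, so a reoperation rule would account for only one of them at six months. The one-year report on six patients shows no more: it is not stated whether the reoperated patients had reached one year or are among the six.
- *As many as nine failures in 20 should be expected.* Nine is roughly the upper confidence limit of the rate times 20. At the observed rate, nine or more of 20 has a probability of about 0.2%.
- *The endpoint wording already makes conversion or repeat surgery a failure at later visits.* Section IV has no such component, so the rule has to be added.

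**Conclusion.** The point stands. The 30-day exit of converted patients and the absence of a denominator or failure rule are plain in the text. Retention of reoperated patients is a reasonable inference, no more. Following the plan as written can make later MR results look better than the device achieved.

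At the first study's reoperation rate the difference is about 15 percentage points at 12 months: 100% under either unstated convention, against 85%. That rests on two events in 13 patients, on a rate that carries over to this study's wider range of leaflet disease, and on good MR grades in all other patients and after all repairs. What changes is the reported durability figure and its denominator. The correction is cheap and is best made before results are known.

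**What to change.** In Section X:

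1. State that the 6-, 12- and 24-month MR tables use as denominator all patients in whom a Harpoon procedure was attempted and the device was used. List separately, with reasons, enrolled patients whose procedure was not started or was interrupted before device use.
2. Show conversion or mitral reoperation up to each visit as its own category, carried forward as device-performance failure. Include the patients who exit at 30 days. Say that this is an added rule and not part of the endpoint wording in Section IV.
3. List any MR grade obtained after mitral surgery, but do not count it as a device result.
4. Report the number and timing of conversions and mitral reoperations at each visit.

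In Section VII, reconcile Treatment Procedure/Assessments with Follow-up Procedures/Assessments, so that the follow-up path of a delayed conversion is clear.

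The cost is a few sentences in Sections VII and X. No new visits or data are needed, because the failure is known when the patient exits or is reoperated. Reported success rates will be slightly lower.
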